2.2.2 KNOWN POTENTIAL BENEFITS

The ideal method of bowel preparation for colonoscopy is a combination of effectiveness, safety, ease of self-administration, good patient acceptance and low cost. While current available preparations offer effectiveness and safety at a reasonable level, patient acceptance can still be improved. A bowel cleansing agent such as mannitol, which has a much better flavour than other cleansing agents, requires low volume and is self-administered the morning of the procedure (and thus does not interfere with sleep), is expected to improve patient compliance and thus the success of the procedure.

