	
prevent reaching the valve; transverse, including flexures; and left at the sigmoidal-rectum junction, 15-25 cm from anal margin) of potentially dangerous levels of H₂ and/or CH₄ (>4% Vol and >100% LEL, respectively) during colonoscopy after standard washing and air insufflation for luminal distension.
 
• Incidence of adverse events from the beginning of study drug self-administration.• Proportion of patients with change from baseline considered clinically significant by the Investigator of haematological and chemical parameters (CBC, creatinine, BUN, eGFR, ALT, AST, glucose, electrolytes) 4 hours and 8 hours after completion of study drug self-administration, where clinically significant means that the change causes an additional control or a medical intervention.• Proportion of patients with change from baseline considered clinically significant by the Investigator of vital signs (heart rate, systolic and diastolic blood pressure) measured during visits, as well as clinically significant change of pulse oximetry and heart rate measured during colonoscopy and systolic and diastolic blood pressure measured immediately prior and after colonoscopy, where clinically significant means that the change causes an additional control or a medical intervention. Of note, clinically significant changes of systolic and diastolic blood pressure measured during colonoscopy will also be reported if considered clinically significant by the Investigator.
To evaluate adherence to and acceptability of bowel preparation with mannitol and with Moviprep®.	
• Adherence: study drug completely taken, partially taken, not taken• Bowel Cleansing Impact Review (BOCLIR) (only at Italian centres)• Ease of use: NRS (0 = very difficult to 10 = very easy)• Taste: NRS (0 = terrible to 10 = very good)• Willingness to reuse the preparation (yes/no)

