The BOCLIR is a measure of the acceptability and tolerability of bowel cleansers consisting of three unidimensional scales (satisfaction, symptoms and activity limitations) with good psychometric and scaling properties. Item responses are summed to provide scale scores. In the final validated Italian version of BOCLIR, the satisfaction scale contains eight items (each item using a 4-point scale from 0 to 3) and the score ranges from 0 (highly satisfied) to 24 (highly dissatisfied). The symptoms scale includes 14 items (each item using a 4-point scale from 0 to 3) and the score ranges from 0 (no symptoms) to 42 (severe symptoms). The activity limitations scale is made up of 12 items (each item using a 4-point scale from 0 to 3) and the score ranges from 0 (no effect on activities) to 36 (activities greatly affected). The total score is the sum of the three scales and ranges from 0 to 102. Patients who report a worse experience in terms of the three factors score higher on the BOCLIR scale. The BOCLIR allows accurate assessment of patient response to bowel cleansing preparations (*Doward et al., 2013*). The BOCLIR questionnaire is completed at Visit 4 by patients following completion of study drug self-administration but prior to colonoscopy at Italian sites because only the Italian language version is validated for use in clinical trials.

- Patient reported outcomes

The following information will be collected from the patient through questionnaires at Visit 4 following completion of the bowel cleansing procedure but prior to colonoscopy:

- Adherence: study drug completely taken, partially taken, not taken
- Ease of use: NRS (0 = very difficult to 10 = very easy)
- Taste: NRS (0 = terrible to 10 = very good)
- Intention to reuse the preparation (yes/no)
- Concomitant medications are collected at each visit, drugs for colonoscopy at Visit 4.
- The incidence of adverse events will be recorded.

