9.3 POPULATIONS FOR ANALYSES

The following populations will be used for the statistical analyses:

- Safety set: all patients who take the study preparation, even only partially. Patients will be analysed according to the study drug dose actually received.
- Modified Safety set: all patients who take the study preparation, even only partially, and who do not meet significant protocol violations that regard inclusion/exclusion criteria. Patients will be analysed according to the study drug dose actually received.
- PK population (only for the pharmacokinetic sub-study): all randomized patients who complete the mannitol treatment and have at least one PK assessment, regardless of the outcome of colonoscopy. Patients will be analysed according to the study drug dose actually received.
- Full Analysis Set (FAS): all randomized patients who take the study preparation, even only partially, undergo the colonoscopy, and have a BBPS available for at least one colon segment after standard washing and air insufflation for luminal distension. According to the Intention to Treat (ITT) principle, patients will be analysed according to the study drug dose assigned at randomization.
- Per protocol (PP): all randomized patients who meet the following criteria:
 - Treatment with the study drug completed.
 - Colonoscopy completed adequately in absence of pathological obstruction that prevents reaching the right colon, including the cecum (i.e. endoscope does not find obstacles other than faecal material) and without acute deterioration of general conditions causing procedure suspension.
 - Bowel cleansing assessment and gas measurement are available for all colon segments after standard washing and air insufflation for luminal distension.
 - No significant protocol violations that regard inclusion/exclusion criteria or that can condition evaluations.

Patients will be analysed according to the study drug dose actually received.

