- Adenoma detection rate
- Caecal intubation rate
- Ottawa bowel preparation scale

Confidence intervals for proportions will be calculated based on the Wald method.

Adherence and acceptability

The analysis of adherence variables will be performed on the FAS. No between-group inferential analysis will be performed. Descriptive statistics and Wald 95% CIs of the between-group differences will be applied on the following variables:

- Bowel Cleansing Impact review (BOCLIR) scales
- Adherence
- NRS score for ease of use and taste
- Willingness to reuse the preparation

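### Phase III adherence is analysed on a set that excludes every patient who took no study drug, so the reported rates and between-arm difference do not describe the randomised patients

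*Combined protocol and SAP*

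**What the plan says.** Section 3 makes adherence part of a phase III objective: "To evaluate adherence to and acceptability of bowel preparation with mannitol and with Moviprep". The endpoint is "Adherence: study drug completely taken, partially taken, not taken".

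Section 9.4.1 (Phase III, Adherence and acceptability) fixes the analysis set: "The analysis of adherence variables will be performed on the FAS". The planned output is "Descriptive statistics and Wald 95% CIs of the between-group differences will be applied on the following variables", with no between-group inferential analysis.

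Section 9.3 defines the FAS as "all randomized patients who take the study preparation, even only partially, undergo the colonoscopy, and have a BBPS available for at least one colon segment", assessed after washing and air insufflation and analysed by assigned treatment. The Safety and modified Safety sets also require at least partial intake, and the PP set requires completed treatment. The PK population belongs to phase II only.

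Randomisation and dispensing take place at Visit 3, up to 7 days before colonoscopy (section 4.1.3). Adherence is collected by patient questionnaire at Visit 4, "following completion of the bowel cleansing procedure but prior to colonoscopy" (section 8.1.3). Section 5.3 counts as a screen failure anyone who consents and does not go on to start treatment. As worded, this includes randomised patients.

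**The concern.** One of the three outcome levels cannot occur in the set used to report it. A patient can be randomised, receive the drug and never take it. That patient is the clearest case of non-adherence, yet is in neither the numerator nor the denominator. A patient who stops part-way and does not have the colonoscopy is lost too, because the FAS also requires the procedure and a score.

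Adherence is a stated objective and part of the rationale for the product. Section 2.2.2 says a preparation such as mannitol "is expected to improve patient compliance and thus the success of the procedure". Patients know their treatment, and the regimens differ (a single same-day drink against two split litres), so refusal and early stopping could differ by arm. Section 2.1 cites a trial of other PEG regimens in which 4 of 91 patients stopped in one arm and 15 of 96 in the other. A reader of the phase III report would take the adherence rates and their difference as describing randomised patients, and they would not.

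**Working it through.** **Set logic.** FAS membership requires some intake; the lowest adherence level means no intake. The two have no patient in common. For any data, that level is 0/n in each arm, its difference is 0 and its Wald interval has zero width. No other set in section 9.3 can contain such a patient.

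**Denominator.** The plan states no adherence figure, so only the arm size can be reproduced. With 0.85 in both groups, margin 0.08, one-sided 0.025 and 80% power (section 9.1): 2 × 0.85 × 0.15 × (1.960 + 0.842)² / 0.08² = 312.7, so 313. Allowing 10% losses, 313/0.90 = 347.8, so 348. Both match the plan. The allowance is 348 − 313 = 35 per arm for dropouts and major deviations together; the plan does not say how many would be never-takers.

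**Formula.** Let p be the share taking part of the drug, n the share taking none, and c the share of partial takers who are not scoped. Suppose first that every complete taker is in the FAS.

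- True non-adherence = p + n
- FAS non-adherence = p(1 − c) / (1 − n − pc)

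All rates below are assumptions; the documents give none.

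| Mannitol p, n | Moviprep p, n | c | True | FAS | Difference, true → FAS (points) |
|---|---|---|---|---|---|
| 2%, 1% | 3%, 3% | 0 | 3.0% vs 6.0% | 2.0% vs 3.1% | 3.0 → 1.1 |
| 2%, 1% | 3%, 3% | 0.3 | 3.0% vs 6.0% | 1.4% vs 2.2% | 3.0 → 0.8 |
| 2%, 1% | 5%, 1% | 0 | 3.0% vs 6.0% | 2.02% vs 5.05% | 3.00 → 3.03 |
| 2%, 3% | 4%, 1% | 0 | 5.0% vs 5.0% | 2.1% vs 4.0% | 0 → 2.0 |

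First row: 0.02/0.99 = 2.0% and 0.03/0.97 = 3.1%. Last row: 0.02/0.97 = 2.06% and 0.04/0.99 = 4.04%. The difference can be shrunk, left alone or created.

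**Counts on 348 randomised in one arm,** with about 5% partial intake among takers and all takers scoped:

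| Never-takers (assumed) | Non-adherent, FAS | Non-adherent, all randomised |
|---|---|---|
| 0 | 17/348 = 4.9% | 17/348 = 4.9% |
| 3 | 17/345 = 4.9% | 20/348 = 5.7% |
| 7 | 17/341 = 5.0% | 24/348 = 6.9% |
| 17 | 17/331 = 5.1% | 34/348 = 9.8% |
| 35 | 16/313 = 5.1% | 51/348 = 14.7% |

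The FAS figure barely moves while the all-randomised figure triples. If never-takers differ by arm (3 vs 17, with 10 partial takers in each), the FAS gives 10/345 − 10/331 = −0.1 points. All randomised gives 13/348 − 27/348 = −4.0 points.

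**The opposite direction.** If the 35 patients outside the FAS were all complete takers without a colonoscopy or score, the FAS would give 16/313 = 5.1% against a true 16/348 = 4.6%.

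**The case against.** The strongest objection is that little hangs on this. Adherence is descriptive in phase III, has no decision rule and cannot change the non-inferiority result. That stands, and it limits the point to the reporting of a secondary objective.

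Second, never-starters are not wholly undocumented. Section 5.3 asks for minimum screen-failure details, sections 7.2 and 7.3 record withdrawal reasons and loss to follow-up on the eCRF, and section 6.2.1 requires drug records for each subject. This is true, but none of these promises a count by arm within the adherence analysis. Section 5.3 would instead move a randomised refuser out of the trial population.

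Third, the size rests on assumed rates. This also stands. Section 2.1 cites a study with 97% compliance, so the effect may be small. With 3% vs 6% on 348 per arm, the Wald half-width is 1.96 × √[(0.03 × 0.97 + 0.06 × 0.94)/348] = 3.1 points. The interval would include 0 even on the full set, and the 1.9 to 2.2 point loss in the first two rows above is smaller than that half-width.

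Fourth, a reader might infer that the FAS always understates non-adherence, or always shrinks a real difference between arms. The documents support neither. Complete takers who are not scoped push the rate up, and the last two rows of the first table show a difference left unchanged and one created from nothing.

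**Conclusion.** The point holds as a matter of definition. The set named for phase III adherence cannot contain patients who took nothing, and it also drops partial takers who were not scoped. The rates and the between-arm difference with its Wald interval therefore do not describe adherence among randomised patients.

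The magnitude is not determined by the documents. It is zero if all randomised patients take some drug and enter the FAS. Assuming about 5% partial intake, understatement within an arm is about 1 to 5 points for 3 to 17 never-takers, and nearly 10 points if all 35 allowed losses were never-takers. The direction depends on who is missing: never-takers and unscoped partial takers lower the reported rate, while unscoped complete takers raise it. Nothing in the documents shows that the choice favours either arm. The primary analysis is unaffected. The change is worth making because adherence is a stated objective and the error comes from a written rule.

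**What to change.** - **Section 9.4.1, phase III:** analyse the adherence variable on all randomised patients to whom study drug was dispensed, by assigned arm. Count those who took none at the lowest level, and those who stopped part-way at the middle level whether or not they were scoped. Give the difference and 95% CI on this set, with the FAS result as supportive.
- **Section 9.3 and the synopsis:** add this analysis set.
- **Data source:** for patients without a Visit 4 questionnaire, take intake from drug accountability and returned drug (sections 6.2.1 and 6.3), the intake time form (section 4.1.3) and the recorded withdrawal reason (section 7.2). Show the remainder as unknown, by arm.
- **Section 5.3:** limit screen failures to patients who were not randomised.

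Leave ease of use, taste and willingness to reuse on the FAS; no error has been shown there.

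The cost is wording in four places and one extra table, with no new visit. The downside is that some patients will be unknown, possibly more than a few, because adherence is collected at a visit that non-starters may not attend.

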9.4.2 ANALYSIS OF SAFETY

Descriptive statistics both on the Safety set and on the modified Safety set for both phase II and phase III will be performed on:

- Proportion of patients with presence/absence of potentially dangerous levels of H₂ and CH₄ (>4% Vol and >100% LEL, which is equal to 5% Vol, respectively) in each colon segment during colonoscopy after standard washing and air insufflation for luminal distension.
- H₂, CH₄ and O₂ concentrations, expressed in % Vol, in each colon segment (right, between ileocecal valve and appendix or as close as possible to the ileocecal valve in case of obstacles that prevent reaching the valve; transverse, including flexures; and left, at the sigmoidal-rectum junction, 15-25 cm from anal margin) after standard washing and air insufflation for luminal distension. CH₄ (% LEL) will be converted into % Vol by means of the following formula: (CH₄ in % LEL)*5/100.
- Proportion of patients with adverse events and the number and types of events occurred.

- Proportion of patients with change from baseline (Visit 2) considered clinically significant by the Investigator of haematological and chemical parameters, where clinically significant means that the change causes an additional control or a medical intervention.
- Proportion of patients with change from baseline (Visit 2) considered clinically significant by the Investigator of vital signs (heart rate, systolic and diastolic blood pressure) (phase III only) and proportion of patients with clinically significant change of pulse oximetry and heart rate measured during colonoscopy, as well as systolic and diastolic blood pressure measured immediately prior and after colonoscopy (phase III only), where clinically significant means that the change causes an additional control or a medical intervention. Of note, clinically significant changes of blood pressure measured during colonoscopy will also be reported if considered clinically significant by the Investigator.

The analyses on the modified Safety set will be considered as supportive.

For phase III only, descriptive statistics will be provided on intestinal gas concentrations following the introduction of the colonoscope in the rectum/sigma before standard washing and air insufflation.

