2.2 RISK/BENEFIT ASSESSMENT

2.2.1 KNOWN POTENTIAL RISKS

Mannitol

The safety and tolerability of mannitol were reported in 433 patients receiving mannitol in comparative clinical trials. The most frequent adverse events (AE) reported in these trials were serum electrolyte changes, nausea and abdominal pain. Other AE's were vomiting, abdominal distension and increased haematocrit. In general safety and tolerability were comparable between mannitol and its comparators.

Intestinal gas levels were measured in 127 patients receiving mannitol in five clinical trials conducted between 1981 and 2016. In general, higher gas levels, especially of H₂, were measured in the mannitol patients if the procedure was performed without air insufflation, otherwise no differences were reported between mannitol and the comparators. No differences were found in O₂ and CH₄ levels.

A recent clinical study evaluated intestinal gas concentrations in three intestinal segments during introduction and withdrawal of the colonoscope with minimum air insufflation or suction. Intermittent infusions of small quantities of water were used as necessary. The study did not find elevated levels in any of the 50 patients examined with mannitol (*Paulo et al., 2016*).

To ensure patient safety in this study, colon H₂ and CH₄ concentrations will be measured during colonoscopy and all electrosurgical procedures will be avoided should gas concentrations reach potentially dangerous levels.

Anaphylactic/anaphylactoid reactions, as well as other hypersensitivity/infusion reactions have been reported with mannitol. Patients with known hypersensitivity to mannitol will be excluded from the study.

Patients with pre-existing renal disease, or those receiving potentially nephrotoxic drugs, are at increased risk of renal failure following administration of mannitol. Patients with severe renal disease will be excluded from this study.

Accumulation of mannitol (due to insufficient renal excretion) and dehydration due to diarrhoea may result in hypervolemia, overexpansion of extracellular fluid, which may lead to or exacerbate existing congestive heart failure. Patients with severe symptomatic congestive heart failure or recent ischemic heart disease will be excluded from this study.

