4 STUDY DESIGN

4.1 OVERALL DESIGN

This is a phase II/III, international, multicentre, randomized, parallel-group, endoscopist-blinded study that combines a phase II dose-finding study/pharmacokinetic sub-study with a phase III non-inferiority efficacy study (see [Figure 4-1](#)). The population for phase III will not include the patients who participated in phase II.

Figure 4-1 Study design

In both phases, the study drugs will not be blinded, but all endoscopists performing study colonoscopies will not be aware of group allocation; patients and site personnel involved in the randomization of the patient and management of the study drugs will be instructed not to disclose group allocation to the endoscopists. Experienced endoscopists will undergo specific training to decrease inter-observer variability in the evaluation of bowel cleansing and to refine intestinal gas measurement techniques.

Details of all the assessments to be performed are available in the schedule of activities (SoA) in [Section 1.2](#) and in [Section 8](#).

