5.2 EXCLUSION CRITERIA

An individual who meets any of the following criteria will be excluded from participation in this study:

1. Pregnancy or breast feeding. Females of childbearing potential must have a negative pregnancy test at Visit 2 and must practice one of the following methods of birth control throughout the study period (unless postmenopausal or surgically sterile, or whose sole sexual partner has had a successful vasectomy): oral, implantable, or injectable contraceptives (for a minimum of three months before study entry) in combination with a condom; intrauterine device in combination with a condom; double barrier method (condom and occlusive cap with spermicidal foam/gel/film/cream/suppository).
2. Severe renal failure: glomerular filtration rate (eGFR) < 30 ml/min/1.73 m² estimated by means of simplified MDRD equation.
3. Severe heart failure: NYHA Class III-IV.
4. Severe anaemia (Hb ≤ 8 g/dl).
5. Severe acute and chronically active Inflammatory Bowel Disease; patients in clinical remission (Crohn's Disease Activity Index - CDAI < 150 for Crohn Disease (*Best et al., 1976*) and Partial Mayo Score ≤ 2 for Ulcerative Colitis (*Schroeder et al., 1987*) are allowed.
6. Chronic liver disease Child-Pugh class B or C.
7. Electrolyte disturbances (Na, Cl, K, Ca or P out of normal ranges)
8. Recent (< 6 months) symptomatic acute ischemic heart disease.

9. History of significant gastrointestinal surgeries, including colon resection, sub-total colectomy, abdominoperineal resection, de-functioning colostomy or ileostomy, Hartmann's procedure and other surgeries involving the structure and function of the colon.
10. Use of laxatives, colon motility altering drugs and/or other substances (e.g. simethicone) that can affect bowel cleansing or visibility during colonoscopy within 24 hours prior to colonoscopy.
11. Suspected bowel obstruction or perforation.
12. Indication for partial colonoscopy.
13. Patients who have received an investigational drug or therapy within 5 half-lives of the first visit.
14. Patients previously screened for participation in this study.
15. Hypersensitivity to the active ingredients or to any of the excipients of the study drugs.
16. Contraindications to Moviprep® (only for phase III).

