6.2 PREPARATION/HANDLING/STORAGE/ACCOUNTABILITY

6.2.1 ACQUISITION AND ACCOUNTABILITY

Study drugs will be provided by the Sponsor. An unblinded Investigator, or a pharmacist or other appropriate individual who is designated by the Investigator, will maintain accurate records of study drug delivery to the study site, the inventory at the site, the use for each subject, and the return to the sponsor or alternative disposition of unused products.

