8.1.4 LABORATORY TESTS (PHASE II AND PHASE III)

Standard urinalysis, haematological and blood chemistry tests will be performed at Visit 2 (pre-colonoscopy visit) and at Visit 4, 4 hours \pm 30 minutes and 8 hours \pm 30 minutes after the end of study drug self-administration. A blood beta hCG pregnancy test is required for women of childbearing potential at Visit 2. The lab tests to be performed are listed in the Table below and are to be performed in both phase II and phase III.

Laboratory Assessments		
Haematology	Serum chemistry	Urine analysis

• Haematocrit (Hct)• Haemoglobin (Hb)• Mean corpuscular haemoglobin (MCH)• Mean corpuscular haemoglobin concentration (MCHC)• Mean corpuscular volume (MCV)• Platelet count• Red blood cell (RBC) count• White blood cell (WBC) count with differential	
• Alanine aminotransferase (ALT)• Aspartate aminotransferase (AST)• Total bilirubin• Direct bilirubin• Blood Urea Nitrogen (BUN)• Creatinine• eGFR estimated by means of simplified MDRD equation• Potassium• Sodium• Phosphorus• Calcium• Chloride• Glucose• Pregnancy test (beta hCG at Visit 2)	
• Appearance• pH• Protein• Glucose• Ketone bodies• Indicators of blood and WBCs• Specific gravity*• Urobilinogen

*Urine specific gravity may decrease because of osmotic diuresis caused by mannitol. The event is to be considered expected.

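### The only laboratory-specific safety item in Section 9.4.2 counts changes the Investigator acted on, with study drugs open; summaries of the measured values should be added

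*Combined protocol and SAP*

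**What the plan says.** Section 9.4.2 plans descriptive statistics on the Safety set, with the modified Safety set as supportive. Its single laboratory-specific item is the proportion of patients with a change from Visit 2, one "considered clinically significant by the Investigator of haematological and chemical parameters, where clinically significant means that the change causes an additional control" (interventions also count). Section 3 defines the endpoint in the same way, for 4 h and 8 h after study drug: "Proportion of patients with change from baseline considered clinically significant by the Investigator of haematological and chemical parameters". No numeric criterion is given. No summary of values, change from baseline, shift table or out-of-range count is listed.

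Gas in the same list is treated differently. It is analysed against fixed thresholds and also as measured concentrations.

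On blinding, Section 4.1 says that "the study drugs will not be blinded, but all endoscopists performing study colonoscopies will not be aware of group allocation". Section 6.2.1 names "An unblinded Investigator, or a pharmacist or other appropriate individual who is designated by the Investigator" for drug accountability. No blinded review of laboratory results is described.

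The values are collected. Section 8.1.4 states: "Standard urinalysis, haematological and blood chemistry tests will be performed at Visit 2 (pre-colonoscopy visit) and at Visit 4", with the Visit 4 samples at 4 h and 8 h. The panel includes sodium, potassium, chloride, calcium, phosphorus, creatinine, eGFR and haematocrit. Exclusion criterion 7 in Section 5.2 bars patients whose electrolytes are outside normal ranges.

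**The concern.** The reported variable is a decision to act. Whether a patient is counted depends on what happened to the laboratory value and on whether someone at the site repeated a test or intervened. Where that person knows the treatment, a difference in readiness to act on a new preparation and on a familiar one can create a difference between arms, or hide one. This is detection (ascertainment) bias; it has nothing to do with how patients were allocated.

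The matter deserves attention because electrolyte change is a recognised risk here. Section 2.2.1 gives the most frequent adverse events of mannitol in earlier comparative trials as "serum electrolyte changes, nausea and abdominal pain", and says that electrolyte levels will be followed during the study. Section 8.2 makes acute electrolyte derangement an event of particular interest. Safety and tolerability of mannitol is a phase III objective. Blood is drawn three times per patient, yet if the plan is followed exactly, no listed variable shows how the values moved.

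**Working it through.** **1. The plan's own figures.** The documents state no figure for the laboratory endpoint. The group size used below comes from the primary endpoint in Section 9.1 and reproduces: n = 2 × 0.85 × 0.15 × (1.96 + 0.84)² / 0.08² = 312.7 (computed with unrounded normal quantiles), so 313 per group. With 10% dropout, 626 / 0.90 = 695.6, so 696 in total and 348 per group.

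**2. Routes by which a laboratory change can reach the safety tables.**

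| Route | Where | Depends on Investigator judgement or recording? |
|---|---|---|
| Clinically significant change | 9.4.2, Section 3 | Yes: requires that the change led to a control or intervention |
| Adverse event | 9.4.2 with 8.2 and 8.3.1 | Yes: the Investigator records the event; no control or intervention is required |
| Urine specific gravity out of range, collected as an expected adverse event | 2.2.1, 8.1.4 | Tied to the normal range, but not an electrolyte |
| General rule for continuous data | 9.4 | Sets the format only; names no laboratory variable |

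No listed route reports serum electrolytes independently of a judgement or a recording decision.

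**3. Size, under assumed rates.** The documents give neither an out-of-range rate nor an action rate, so every rate here is an assumption.

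Recorded rate = (true out-of-range rate) × (probability that staff act).

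Wald 95% half-width = 1.96 × √[p₁(1 − p₁)/348 + p₂(1 − p₂)/348].

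*Moderate case.* True rate 10% in both arms, action 30% v 15%:
- recorded: 0.10 × 0.30 = 3.0% and 0.10 × 0.15 = 1.5%, about 10 v 5 patients;
- difference 1.5 points; half-width 1.96 × √[(0.03 × 0.97 + 0.015 × 0.985)/348] = 2.2 points.

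*Range.* Equal true rates, action 50% v 30%:

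| True rate, both arms | Recorded | Spurious difference (points) | 95% half-width (points) |
|---|---|---|---|
| 5% | 2.5% v 1.5% | 1.0 | 2.1 |
| 10% | 5.0% v 3.0% | 2.0 | 2.9 |
| 20% | 10.0% v 6.0% | 4.0 | 4.0 |
| 30% | 15.0% v 9.0% | 6.0 | 4.8 |

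*No bias.* Equal action rates (50% v 50%) give a difference of 0 at every true rate.

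*Masking.* True 20% v 10%, action 30% v 60%: recorded 6.0% v 6.0%. Counting the values directly would show 10 points ± 5.3.

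**4. Precision of a direct count.** For an out-of-range rate of 10% in each arm, 1.96 × √(2 × 0.10 × 0.90/348) = 4.5 points. For rates of 5% to 30% the half-width runs from 3.2 to 6.8 points.

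**The case against.** The strongest reply is that laboratory safety is not confined to this one item. Section 9.4.2 also analyses adverse events, Section 8.3.1 lets an abnormal laboratory finding count as one, and such an event need not have led to a control or intervention. This stands: it would be too strong to say that the plan's only laboratory safety information is the action count. But the second route still depends on what the Investigator records.

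Four other strong readings are tempting, and the documents do not support them as stated.

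- *The laboratory assessor is unblinded.* No section says who judges Visit 4 results, and the unblinded Investigator of Section 6.2.1 is named only for accountability. Knowledge of allocation is a likely inference from Section 4.1, not a stated fact.
- *Any out-of-range electrolyte at Visit 4 is new, because of exclusion criterion 7.* This is safe only for eligible patients. The Safety set keeps anyone enrolled in breach of the criterion; only the modified Safety set removes significant eligibility violations. Visit 2 may also be up to seven days before colonoscopy, so a new excursion need not be due to the drug.
- *A formal safety conclusion is compromised.* Section 9.4.2 is descriptive, with no safety test and no between-arm interval for laboratory items. Phase II has no Moviprep arm, so the argument about a new and a familiar preparation does not apply there.
- *The fix needs only data already stored.* The tests are listed, but nowhere do the documents say that site normal ranges are captured. The centralised laboratory is named only for mannitol concentrations, and with about 50 phase III sites the ranges may differ.

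It is also fair to say that a single proportion with any electrolyte out of range would be a blunt measure, since it mixes trivial with important excursions and ignores direction.

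**Conclusion.** The point holds as a cheap improvement. Section 9.4.2 reports electrolyte safety only through routes that depend on Investigator judgement or recording, although numeric values are collected at Visit 2, 4 h and 8 h and gas in the same list is analysed from its measurements. The phase III comparison is therefore open to detection bias. Its direction cannot be known from the documents.

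Its size cannot be known either. Under the assumed rates it ranges from nothing, when both arms are acted on equally, to a spurious 6 points, and opposite readiness to act could hide a true 10-point difference. In the moderate case the spurious 1.5 points is smaller than its own 95% half-width of 2.2. The sample size, the primary analysis and all formal tests are unaffected. The conclusion assumes that the person judging laboratory changes usually knows the treatment.

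**What to change.** Add to Section 9.4.2:

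- descriptive summaries of measured values, and of change from Visit 2, at 4 h and 8 h for Na, K, Cl, Ca, P, creatinine/eGFR and haematocrit;
- shifts from in range at Visit 2 to below or above the local laboratory range, by electrolyte and direction, so that patients already out of range at baseline are not counted as new.

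Present these by dose group in phase II, as description only, and by arm with the difference and 95% CI in phase III. Section 9.4.1 already gives differences with intervals, without inferential testing, for the secondary efficacy variables. Use both the Safety set and the modified Safety set. Keep the Investigator-judged proportion as an additional description.

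The cost is a few tables and one check: that each site's normal ranges are captured, which the documents do not state. No new samples, visits or patients are needed. Plasma osmolality is left out because Section 2.2.1 mentions it but the test list in Section 8.1.4 does not include it.
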